4.4.2 Secondary Endpoint 2: Robotically Navigate Device to the Target Aneurysm

Endpoint: Defined as successful advancement of device TO the target aneurysm robotically. Specifically, success if defined as all guidewires, microcatheters, coils, and stents that may have been used must all have been able to navigate TO the target aneurysm as identified on CRF 9 CorPath GRX Intervention Assessment CRF. Likewise, failure is any single instance where one or more of those listed items were unable to navigate to target lesion.

Subjects to Include: Analysis Cohort

Statistical Analysis: The count and proportion of aneurysms where CorPath was able to navigate TO the target lesion successfully will be calculated along with a 2-sided Clopper Pearson Exact 95% confidence interval.

4.4.3 Secondary Endpoint 3: Robotically Navigate Device into the Target Aneurysm

Endpoint: Defined as successful advancement of device INTO the target aneurysm robotically. Specifically, success if defined as all guidewires, microcatheters, coils, and stents that may have been used must all have been able to navigate INTO the target aneurysm as identified on CRF 9 CorPath GRX Intervention Assessment CRF. Likewise, failure is any single instance where one or more of those listed items were unable to navigate into target lesion.

Subjects to Include: Analysis Cohort

Statistical Analysis: The count and proportion of aneurysms where CorPath was able to navigate INTO the target lesion successfully will be calculated along with a 2-sided Clopper Pearson Exact 95% confidence interval.

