#### CorPath Use Technique

*To obtain proper data for analysis, the following procedure, with associated data collection milestones, is recommended, but in no case, dictates use of the CorPath GRX System in a manner*

*Version Date: May 21, 2021*

*This confidential document is the property of Corindus, Inc. and shall not be reproduced, distributed, disclosed or used without the express written consent of Corindus, Inc.*

*different from that presented in the Operator's Manual.*

**The following CorPath Use Technique guides the Investigator through coiling a cerebral aneurysm with the CorPath GRX System.**

1. Obtain arterial access using conventional technique. Record sheath insertion time.
2. Once arterial access is obtained, insert a standard diagnostic catheter using conventional manual technique or guide catheter mounted coaxially over a diagnostic insert catheter.
3. Manually advance the diagnostic select catheter to the parent vessel.
4. Advance guide catheter to desired location in parent vessel and remove wire and diagnostic select catheter. If only diagnostic catheter was used, then remove standard wire and use exchange length guidewire; remove the diagnostic catheter over the exchange wire while maintaining distal wire position. Advance the guide catheter over the exchange wire to the desired location in parent vessel and remove wire.
5. The Investigator will specify which devices will be delivered robotically.
6. Manually advance microcatheter to tip of guide catheter in the parent vessel.
7. Manually insert exchange length guidewire and attach COPILOT bleed back control valve to the microcatheter.
8. Record microcatheter "insertion" time.
9. Load the microcatheter and exchange length guidewire in the CorPath GRX cassette.
10. Using the CorPath System, advance guidewire and microcatheter independently to target treatment area. The Active Device Fixation (ADF) technIQ automated movement can be enabled to keep the guidewire in place during microcatheter movement.
11. With microcatheter in place, remove guidewire.
12. Advance stent into the COPILOT bleed back control valve and proximal microcatheter slowly and according to stent delivery IFU.
13. Place the stent advancement wire into the Device Track of the CorPath GRX.
14. Advance stent, robotically, to target area. The stent will remain completely sheathed in the microcatheter.
15. Robotically position the stent across target aneurysm.

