4.4.12 Secondary Endpoint 12: Devices Used Robotically

Endpoints: All devices used will be recorded as successful or unsuccessful in conjunction with the CorPath GRX System. Each device used (e.g., guidewire, microcatheter, coil, etc.) is documented on CRF 9 CorPath GRX Assessment form, and an individual component needs to have successfully navigated to the aneurysm, into the aneurysm, and deployed (if applicable) into the aneurysm to be considered successful.

Subjects to Include: Analysis Cohort

Statistical Analysis: The frequency and proportion of devices successfully used that were used with a CorPath GRX System will be summarized along with a 2-sided Clopper Pearson Exact 95% confidence interval.

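### SAP 4.4.3 and 4.4.12 require a stent to go into the aneurysm, while the protocol places it across, so a flawless stent-assisted aneurysm cannot meet the endpoint 3 success rule

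*SAP*

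**What the plan says.** SAP 4.4.2, 4.4.3 and 4.4.4 use one device list and change only the action required. For endpoint 2 every listed device "must all have been able to navigate TO the target aneurysm", which a stent can satisfy. For endpoint 3 the rule becomes "all guidewires, microcatheters, coils, and stents that may have been used must all have been able to navigate INTO the target aneurysm". The matching failure rule is "failure is any single instance where one or more of those listed items were unable to navigate into target lesion", and the result reported is "The count and proportion of aneurysms where CorPath was able to navigate INTO the target lesion successfully", so the unit is the aneurysm.

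SAP 4.4.12 (endpoint 12) scores single devices. It says "Each device used (e.g., guidewire, microcatheter, coil, etc.) is documented on CRF 9 CorPath GRX Assessment form", so stents are covered though not named. A component "needs to have successfully navigated to the aneurysm, into the aneurysm, and deployed (if applicable) into the aneurysm" to be successful. The words in brackets are attached to deployment and not to the step before it.

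In the protocol's CorPath Use Technique (4.8.5), the stent stays sheathed while it is advanced (step 14). Step 15 reads "Robotically position the stent across target aneurysm". It is unsheathed there (steps 16 and 17), the microcatheter and guidewire are then advanced through its struts (step 19), and the coils follow (step 22). Protocol 4.8.6 names reaching the target, crossing it and being delivered into it as three separate outcomes.

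One line points the other way. The list that opens protocol 4.8.5 speaks of deploying treatment devices into the aneurysm, and the line before it explains treatment devices as coils and stents.

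**The concern.** Stent-assisted coiling is one of the two procedures for which patients are admitted, so this is not a rare exception. If a correctly placed stent cannot meet the entry test, endpoint 3 partly reports how many aneurysms received a stent and not how well the robot navigated. The error runs against the device and falls entirely on the stent-assisted cases.

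The loose line in 4.8.5 adds a second problem. One site may record a stent placed across the neck as having gone into the aneurysm and another may not, so the result would also depend on coding habit.

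**Working it through.** **1. The plan's own figure.** The documents give no expected rate for endpoints 3 or 12. The only planning figure used below is the sample size of 108, which comes from primary effectiveness: 80% under the null, 90% expected, at least 80% power, two-sided 95% interval (one-sided 0.025). By the normal approximation:

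n = [(1.960 × √(0.80 × 0.20) + 0.842 × √(0.90 × 0.10)) / 0.10]² = [(0.784 + 0.253) / 0.10]² ≈ 107.4, rounded up to 108.

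An exact check agrees. At least 95 successes of 108 are needed for the Clopper-Pearson lower bound to exceed 80%, and the power at 90% is 81.0%. The figure reproduces and is used here only as a denominator.

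**2. The SAP rules applied to a perfect stent-assisted aneurysm.**

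| Device | Protocol technique | Endpoint 3 entry test | Endpoint 12 entry test |
|---|---|---|---|
| Guidewire, microcatheter | through the struts for coiling (step 19) | can be met | can be met |
| Coils | advanced to the aneurysm and deployed (step 22) | can be met | can be met |
| Stent | across the aneurysm (steps 15 to 17) | cannot be met | cannot be met |

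Endpoint 3 requires every device to pass, so the aneurysm is not a success. Endpoint 12 is per device, so only the stent is lost.

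**3. Ceiling on endpoint 3.** Let s be the stent-assisted share of aneurysms. With faultless navigation throughout, the highest attainable rate is 1 − s. The documents do not give s, so these values are assumptions. The last is the stent-assisted share of one unruptured series in Table 2 (468 of 1406 = 33.3%), used only as an illustration. With one aneurysm per subject and 108 subjects:

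| Assumed s | Stent-assisted | Ceiling as written | After the fix |
|---|---|---|---|
| 10% | 11 | 97/108 = 89.8% | 108/108 = 100% |
| 20% | 22 | 86/108 = 79.6% | 108/108 = 100% |
| 33% | 36 | 72/108 = 66.7% | 108/108 = 100% |

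**4. Effect on endpoint 12.** Assume one guidewire, one microcatheter and k coils per case, plus one stent in a share s. The share of devices unsuccessful by definition is s / (2 + k + s). At s = 0.333:

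- k = 3: 0.333 / 5.333 = 6.2%
- k = 4: 0.333 / 6.333 = 5.3%
- k = 6: 0.333 / 8.333 = 4.0%

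**The case against.** Several points on the other side have force.

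- **CRF 9 is not in the documents.** Both endpoints are scored from it, and it may already have a not-applicable response for stents. A reader might infer that an honest site has to record a failure; that cannot be known without the form. But the SAP does not say how a not-applicable answer would be scored, so the gap in the SAP remains.
- **The failure sentence speaks of inability.** A stent never meant to enter the sac was not unable to do so. Such an aneurysm then fits neither the success nor the failure sentence. That is an undefined outcome and no rescue: in a proportion of successes it still counts as a non-success.
- **The protocol itself uses the looser wording once.** A site that records a stent as deployed into the aneurysm can point to the list in 4.8.5. This makes the scoring ambiguous, but it does not override the step-by-step technique and 4.8.6, which are more specific.
- **The technique is only recommended.** True, but it is the only stent technique described, and nothing describes placing a stent in the sac.

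A reader might also infer that a microcatheter and guidewire used to deliver the stent fail the entry test. The documents do not support this. The technique mentions no separate delivery microcatheter. It refers to one microcatheter throughout, and step 19 re-advances it with the guidewire through the struts.

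**Conclusion.** The SAP's success rules for endpoints 3 and 12 conflict with the protocol's stent technique and need correcting. Taken literally, endpoint 3 cannot exceed 1 − s: about 90%, 80% or 67% for the three assumed shares, and lower still for a larger share. Endpoint 12 loses about 4% to 6% of devices at s = 33%. These are ceilings under assumption, not forecasts. They rest on a stent share and coil counts that the documents do not supply, on one aneurysm per subject (the inclusion criteria allow more), and on stents being coded as not having entered the aneurysm. The text conflict is certain; its effect on the reported rates depends on CRF 9 and on site coding.

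Two stronger readings are tempting. The first is that whole stent-assisted cases fail endpoint 12; they do not, because it is scored per device. The second is that the trial's main conclusion is at risk. It is not: primary effectiveness counts unplanned conversion in stent deployment and has no entry requirement, so its 80% goal and the sample size of 108 stand. Protocol 6.3 makes the secondary endpoints descriptive, without hypotheses. The point should be settled before analysis, but it does not threaten the trial.

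**What to change.** - **SAP 4.4.3:** apply the entry test only to devices meant to enter the sac. Judge stents on crossing the target, as protocol step 15 and 4.8.6 describe.
- **SAP 4.4.12:** extend the if-applicable qualifier to the entry step, and define stent success as navigated to the target and deployed across it.
- **Scoring rule:** state that a step that does not apply to a device is left out of the all-device test and is not counted as a non-success.
- **CRF 9:** check that the form can record crossing and not-applicable for stents, and add a response option if it cannot.
- **SAP 4.4.4:** correct the shared device list at the same time. It requires guidewires and microcatheters to deploy, and its failure sentence goes back to navigation. A short table of device type against reach, cross, enter and deploy would serve all of these sections.
- **Protocol 4.8.5:** bring the opening list into line with the technique steps, so that sites code alike.

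The cost is a few SAP sentences, one wording alignment in the protocol, and at most one response option on CRF 9. It needs no new patients, procedures or assessments.

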4.4.4 Secondary Endpoint 4: Robotically Deploy Therapeutic Device into the Target Aneurysm

Endpoint: Defined as successful DEPLOYMENT of device into the target aneurysm robotically. Specifically, success if defined as all guidewires, microcatheters, coils, and stents that may have been used must all have been able to DEPLOY into the target aneurysm as identified on CRF 9 CorPath GRX Intervention Assessment CRF. Likewise, failure is any single instance where one or more of those listed items were unable to navigate into target lesion.

Subjects to Include: Analysis Cohort

Statistical Analysis: The count and proportion of aneurysms where CorPath was able to DEPLOY into the target lesion successfully will be calculated along with a 2-sided Clopper Pearson Exact 95% confidence interval.

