### Robotically Deploy Therapeutic Device *into* the Target Aneurysm

Defined as successful deployment of therapeutic device into the target aneurysm robotically;

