#### 4.8.5 CorPath GRX Endovascular Procedure Workflow

The protocol allows for the Investigator to perform the following with the CorPath GRX System:

- Navigate a 0.014" guidewire in the neurovascular anatomy;
- Navigate a microcatheter into the neurovascular anatomy robotically;
- Navigate a microcatheter to the aneurysm robotically;
- Navigate treatment devices (coils/stents) to the aneurysm robotically;
- Deploy treatment devices into the aneurysm robotically.

The Investigator should refer to the CorPath GRX System Operator's Manual for a detailed description of the system and relevant techniques.

After arterial access is obtained, the Investigator will specify what devices will be used robotically prior to starting the robotic portion of the endovascular procedure.

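### SAP 4.4.4 scores robotic deployment with success and failure rules that do not complement each other, and it requires guidewires and microcatheters to deploy

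*SAP*

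**What the plan says.** Protocol 3.4 item 4, and the matching entry in the study summary, give the endpoint as "Defined as successful deployment of therapeutic device into the target aneurysm robotically". Protocol 4.8.5 identifies the treatment devices and lists two separate robotic actions for them: "Navigate treatment devices (coils/stents) to the aneurysm robotically" and "Deploy treatment devices into the aneurysm robotically". Guidewire and microcatheter navigation have their own bullets in that list.

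SAP 4.4.4 keeps deployment in its heading, its lead definition and its success rule, under which "all guidewires, microcatheters, coils, and stents that may have been used must all have been able to DEPLOY into the target aneurysm". Its failure rule is different: "failure is any single instance where one or more of those listed items were unable to navigate into target lesion". The statistic is "The count and proportion of aneurysms where CorPath was able to DEPLOY into the target lesion successfully", with a Clopper-Pearson 95% interval, in the Analysis Cohort.

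For comparison, the failure rule in SAP 4.4.2 uses that endpoint's own verb: "failure is any single instance where one or more of those listed items were unable to navigate to target lesion". SAP 4.4.3 (navigation into the aneurysm) has exactly the failure sentence that reappears in 4.4.4.

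**The concern.** A binary endpoint needs a rule that puts every unit in one of two classes. In 4.4.4 the success sentence is about deployment and the failure sentence is about navigation, so an aneurysm that was entered but not fully treated robotically falls between them. A programmer who works from the failure sentence would reproduce endpoint 3 under endpoint 4's name. One who works from the success sentence as written would require deployment of devices that are only navigated and withdrawn.

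At stake is whether one pre-specified measure of robotic performance has a defined value. If the choice between sentences is made once data are in hand, it is post hoc.

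**Working it through.** **Text comparison**

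1. *Verb.* Endpoint 2 fails on navigating to the lesion and endpoint 3 on navigating into it, each matching its own success rule. Endpoint 4 succeeds on deployment but fails on navigating into the lesion. It is the only one of the three whose failure rule belongs to another endpoint, which looks like a copying slip.
2. *Entry and deployment are separate events.* Protocol 4.8.5 lists them separately, and step 22 of the use technique advances coils and then deploys them. Entry without deployment is therefore a possible outcome, and 4.4.4 does not classify it.
3. *Device list.* Step 11 reads "With microcatheter in place, remove guidewire", and step 23 withdraws the microcatheter after embolization. Neither device is left in place, so neither can meet a deployment rule. SAP 4.4.12 handles this by asking for deployment only where applicable; 4.4.4 has no such qualifier.

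**Illustration**

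The plan states no rate for this endpoint, so there is no figure to reproduce. Inputs:
- N = 108, the planned size in SAP 3.2, assuming one target aneurysm per subject.
- r = 5 aneurysms not entered and without full robotic deployment (assumed).
- d = 5 aneurysms entered but with a coil or stent not deployed robotically (assumed).

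Rates under each reading, with Clopper-Pearson 95% intervals:

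| Reading of 4.4.4 | Formula | Result |
|---|---|---|
| Success = not meeting the failure sentence | (N − r)/N | 103/108 = 95.4% (89.5 to 98.5) |
| Deployment rule, coils and stents only, all else a failure | (N − r − d)/N | 98/108 = 90.7% (83.6 to 95.5) |
| Same numerator, unclassified aneurysms dropped | (N − r − d)/(N − d) | 98/103 = 95.1% (89.0 to 98.4) |
| Success sentence taken literally, guidewires and microcatheters included | 0/N | 0/108 = 0% (0 to 3.4) |

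The gap between the first two rows is d/N. With d = 0, 5 or 10 it is 0, 4.6 or 9.3 percentage points (at d = 10 the deployment rule gives 93/108 = 86.1%, 78.1 to 92.0). With d = 0 the first three rows agree. The fourth row does not depend on d.

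**The case against.** The strongest reply is that 4.4.4 does specify deployment. Its heading, lead definition, success sentence and reported numerator all say so. An aneurysm with an undeployed coil is outside the stated numerator, and if the denominator is all aneurysms the rate comes out right whatever the failure sentence says. The heading's reference to a therapeutic device, and the qualifier in 4.4.12, show what was meant by the device list.

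Much of this stands, and it rules out two stronger readings:

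- A reader might infer that the SAP fails to implement the protocol's endpoint and never counts non-deployment against the device. That is true only of the failure sentence taken alone.
- A reader might infer that the rate will be overstated. That follows only if success is programmed as the absence of failure, which the SAP does not say. The literal success sentence errs in the opposite direction.

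Stents complicate the picture further. Steps 15 to 17 of the technique position the stent across the aneurysm and unsheathe it there. A strict reading of navigation into the lesion could therefore count a correctly placed stent as a failure.

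It is also fair that deployment problems are captured elsewhere. An unplanned conversion for coil or stent deployment fails the primary effectiveness endpoint (SAP 4.2), and 4.4.12 counts deployment by device. Neither gives the proportion of aneurysms that 4.4.4 promises.

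What the reply does not remove is the contradiction inside one paragraph. The intent can be guessed, but the written rules do not state it.

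**Conclusion.** The point holds as an internal contradiction. SAP 4.4.4 has success and failure rules that are not complements, leaves entry without deployment unclassified, and applies a deployment test to devices that are not deployed. The protocol's endpoint concerns the therapeutic device only.

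On the assumed counts, four readings of the same paragraph give 95.4%, 90.7%, 95.1% and 0%. These rest on one target aneurysm per subject and on illustrative values of r and d that are not in the documents. CRF 9 is not in the documents either, so the rate that would actually be reported is unknown, and so is the direction of any error.

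The correction should be made before programming, but its reach is small: one descriptive secondary endpoint with no hypothesis or threshold. The primary endpoints and the sample size are unaffected.

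**What to change.** In SAP 4.4.4:

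1. Limit the device list to coils and stents.
2. Replace the navigation wording in the failure sentence with inability to be deployed robotically, so that failure is the complement of success.
3. State that failure includes aneurysms where a failure to reach or enter meant that no coil or stent could be deployed robotically. Without this, an aneurysm in which no coil or stent was used could pass a rule about all devices used.
4. Keep all Analysis Cohort target aneurysms in the denominator.

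The rule should stay with devices used, as the SAP has it. Scoring devices that were planned for robotic delivery would redefine the endpoint and would have to deal with the distinction in Protocol 4.8.7 between planned and unplanned manual conversion.

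The cost is SAP wording and one derivation. No new data are needed if CRF 9 records deployment by device. SAP 4.4.4 and 4.4.12 both presuppose this, but it should be confirmed.

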4.4.5 Secondary Endpoint 5: Overall Procedure Time

Endpoint: Defined as the time measured from the insertion of the access sheath/catheter until the removal of the microcatheter as recorded on the CRF 6 Procedure Data Form CRF.

Subjects to Include: Analysis Cohort

Statistical Analysis: The mean, standard deviation, median, interquartile range, and range along with a 2-sided 95% confidence interval for the mean will be calculated.

4.4.6 Secondary Endpoint 6: Robotic Procedure Time

Endpoint: Defined as the time measured from the first device used robotically until the removal of the microcatheter as recorded on the CRF 6 Procedure Data Form CRF.

Subjects to Include: Analysis Cohort

Statistical Analysis: The mean, standard deviation, median, interquartile range, and range along with a 2-sided 95% confidence interval for the mean will be calculated.

4.4.7 Secondary Endpoint 7: Fluoroscopy Time

Endpoint: Defined as the total fluoroscopy time during the procedure as recorded by the Imaging System on the CRF 6 Procedure Data Form CRF.

Subjects to Include: Analysis Cohort

Statistical Analysis: The mean, standard deviation, median, interquartile range, and range along with a 2-sided 95% confidence interval for the mean will be calculated.

